4.1.2. Secondary Objectives

The secondary objectives of this study are:

- To determine the efficacy of maternal immunization with the RSV F vaccine in reducing the incidence in infants of:
 - RSV LRTI with EITHER severe hypoxemia (SpO_2 < 92% at sea level or < 87% at altitudes > 1800 meters) or the documented use of oxygen by high flow nasal cannula OR a requirement for continuous positive airway pressure (CPAP) or bilevel positive airway pressure (BiPAP) OR Bubble CPAP OR bag-mask ventilation OR intubation with subsequent mechanical (or manual) ventilation OR extracorporeal membrane oxygenation (ECMO), through the first 90 days of life in infants of maternal RSV F vaccinees as compared to placebo recipients. In the event that efficacy is shown through the first 90 days of life, a hierarchical sequence of hypothesis tests will be carried out to examine efficacy at 120, 150, and 180 days of life.
 - RSV LRTI leading to hospitalization through the first 90 days of life in infants of maternal RSV F vaccinees as compared to placebo recipients. In the event that efficacy is shown through the first 90 days of life, a hierarchical sequence of hypothesis tests will be carried out to examine efficacy through 120, 150, and 180 days of life.

The two secondary efficacy objectives will be evaluated in term infants (≥ 37 weeks gestational age at delivery) born to maternal subjects who received a study injection ≥ 2 weeks (14 days) prior to delivery. Infants with multiple RSV episodes meeting a given criterion will be counted

only once, using data from the first episode. Success under the secondary efficacy hypotheses will be achieved by demonstration of a lower bound of a two-sided 95% confidence interval for the estimate of vaccine efficacy which exceeds 0%.

- To describe the immunologic responses to the RSV F vaccine in healthy maternal subjects, in the third trimester of pregnancies deemed to be at low risk of obstetrical complications, through delivery and six months thereafter.
- To describe the transplacental transfer of maternal antibodies specific for RSV and its F protein based on the ratio of levels in maternal and cord blood at delivery.
- To estimate the rate of decay of RSV and F protein-specific antibodies in infants through the first six months of life.
- To develop an immune correlate of risk of the RSV LRTI syndromes in infants based on anti-F protein antibody and/or palivizumab-competitive antibody levels measured in the infant and/or cord blood.

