5.3.2. Per-Protocol Immunogenicity (PP-IMM) Populations

- The PP-IMM Populations will be the primary analysis populations for the immunogenicity analyses.
- PP-IMM for Maternal Subjects (PP-IMM-M) – defined as all maternal subjects who receive the test article and regimen to which they were randomized, provide baseline and delivery (within 72 hours of delivery) serology data, and have no major protocol deviations affecting the primary immunogenicity outcomes as determined and documented by Novavax prior to database lock and unblinding.
- PP-IMM for Infant Subjects (PP-IMM-I) – defined as all infant subjects who: a) are ≥ 37 weeks gestational age at birth, b) are born to maternal subjects who received a study injection as randomized and ≥ 2 weeks prior to delivery, c) have provided a cord blood specimen (or infant blood sample by venipuncture or heel stick within 72 hours of delivery as an acceptable substitute), d) have not received prophylactic treatment with palivizumab between birth and Day 180 after delivery, and e) have no major protocol deviations affecting the primary immunogenicity outcomes as determined and documented by Novavax prior to database lock and unblinding.

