11.1.1. Anti-F IgG ELISA (EU)

The following parameters will be analyzed for maternal subjects.

- GMEU at baseline (pre-vaccination on Day 0) and post-vaccination on Day 14, at delivery, and postpartum on Days 35 and 180 (as applicable).
- GMFR_{Post/Pre} on post-vaccination Day 14, at delivery, and postpartum on Days 35 and 180 (as applicable).
- GMR_{Cord/MS} on the within-maternal-infant pair for cord blood over maternal serum (MS) at delivery, e.g., GMFR Transplacental Transfer Proportion.
- Seroconversion Rate (SCR) – defined as the proportion of subjects with ≥ 2 -fold and ≥ 4 -fold increases in concentration from baseline, calculated as the proportion (%) of subjects in a particular treatment group with a baseline concentration $<$ LLOQ and a post-vaccination concentration $\geq 2 \times$ LLOQ and $\geq 4 \times$ LLOQ, respectively, or a baseline concentration \geq LLOQ and a ≥ 2 -fold and ≥ 4 -fold, respectively, increase in

post-vaccination concentrations. These response rates will be summarized post-vaccination on Day 14, at delivery, and postpartum on Days 35 and 180 (as applicable).

- Seroresponse rate (SRR) – defined as the proportion (%) of subjects in the RSV F treatment group with an increase in antibody level over a specific time period which is greater than the 95th percentile of antibody response in the absence of active vaccine based on the behavior of placebo recipients' sera over the same period. SRR will be analyzed by computing the ratio (post-vaccination/pre-vaccination [Day 0]) at each post-vaccination time-point on Day 14, at delivery, and postpartum on Days 35 and 180 (as applicable). At a given time-point, the 95th percentile of the ratios in the placebo group will be estimated. A subject in any treatment group will be identified as a responder if its ratio is greater than the estimated threshold in the placebo group at the given time-point.

The following parameters will be analyzed for infant subjects:

- GMEU of anti-F IgG in cord blood and on D+14, D+35, D+60, D+90, D+112, and D+180.
- GMR_{AD/Cord} of anti-F IgG EU within-subject ratios after delivery (AD) on D+14, D+35, D+60, D+90, D+120, and D+180 over cord blood value at delivery.

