- SRR for infant subjects will be analyzed at a given time-point by estimating the 95th percentile of the EU levels in the placebo group. An infant subject in any treatment group will be identified as a responder if its EU level is greater than the estimated threshold in the placebo group at the given time-point.

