11.1.4. Infants Antibody Decay Modeling

To estimate the decay of antibody levels in per protocol infants (PP-IMM-I) that result from RSV F protein vaccine immunization in pregnant women, the log10 transformed antibody

levels will be used as the independent variable and the actual age of infant subjects in days at the time of sample collection as the exploratory variable in the regression analysis. The estimated slope will be used to estimate the half-life as $\log_{10}(2)/\text{slope}$ with the corresponding 2-sided 95% confidence interval. All observed values, except for the measures reported as < LLOQ, for each time-point and infant cohort (Phlebotomy Cohort 1, Cohort 2, and Cohort 3) will be pooled to assess the persistence of anti-F IgG antibody, PCA, and/or MN levels over time. Since values reported as < LLOQ do not provide the exact time when the values crossed the LLOQ, they will be excluded from the half-life estimation. All measurements from subjects with at least two \geq LLOQ measures will be included in the analysis. A conventional first order antibody decay model will be used for analysis. A second order or other, more complex, antibody decay model may be further developed to explain the rate of decay of antibody levels in the infants in the study, albeit the dataset may not be sufficiently rich to support more complex models.

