11.1.5. Immune Correlate of Risk of the RSV LRTI Syndromes in Infants

Analyses will be performed to attempt to identify a correlate of risk (CoR) for the RSV LRTI syndromes in infants based on anti-F IgG and/or PCA levels measured in the infant and/or cord blood and the maternal subjects at Day 14 post-vaccination and delivery. For the purpose of this analysis, the CoR is defined as a general inverse relationship between the level of an immune response parameter before the onset of the first episode of a RSV infection and the RSV disease status. RSV immune measure(s) will be tabulated for each primary and secondary efficacy disease endpoint status for each treatment group and for the combined treatment groups. Qin et al. define a surrogate of protection (SoP) as a CoR that reliably predicts a vaccine's level of protective efficacy on the basis of differences between the vaccinated and unvaccinated groups' immunological measurement(s). Appropriate SoP validating methods as proposed in Qin et al. will be used to explore if the chosen CoR is a potential SoP [Qin 2007].

Two sets of graphs will be created for each primary and secondary efficacy disease endpoint status as screening tools to identify CoRs that are potential SoPs for further assessment.

The first set, which will comprise graphs for each endpoint and each time-point, will show cumulative distribution functions displaying the level of anti-F IgG and PCA levels for the combined treatment group and for each treatment group separately.

The second set, which will consist of receiver operating curves (ROC), will have six graphs for each endpoint, one for each marker and blood pair. If the clinicians consider the area under the ROC curve sufficiently high, the marker will be deemed a CoR. As a rule of thumb, markers with areas of 0.9 and above are considered excellent while those with areas between 0.8 and 0.9 are considered good [Pepe 2004]. Marker and blood pairs with areas under the ROC curve of at least 0.8 will be deemed candidate CoRs.

The maximum values of Youden's J Index (sensitivity + specificity -1), will be used as a first pass at selecting a cut-off value defining the level of the CoR that will be used to explore whether the CoR is a surrogate of protection. The Index assigns equal weight to sensitivity and

specificity. Different weightings may be explored if Novavax and/or external clinician experts judge equal weighting inappropriate.

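### The infant antibody half-life and the infant seroresponse cut-off keep samples drawn after the infant's own confirmed RSV infection, which lengthens the half-life and raises the late cut-off

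*SAP*

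**What the plan says.** The SAP lists decay as a secondary objective (4.1.2): "To estimate the rate of decay of RSV and F protein-specific antibodies in infants through the first six months of life". Section 11.1.4 narrows the target to antibody levels "that result from RSV F protein vaccine immunization in pregnant women". It then regresses log10 level on age, pooling "All observed values, except for the measures reported as < LLOQ, for each time-point and infant cohort", for infants with at least two values at or above LLOQ.

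For the infant SRR, SAP 11.1.1 takes the 95th "percentile of the EU levels in the placebo group" at each visit. An infant in either arm is a responder if its level is "greater than the estimated threshold in the placebo group at the given time-point". Sections 11.1.2 and 11.1.3 apply the same parameters to PCA and microneutralization. The ratio to cord blood is the GMR "of anti-F IgG EU within-subject ratios after delivery (AD) on D+14, D+35, D+60, D+90, D+120, and D+180 over cord blood value at delivery".

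The infant per-protocol immunogenicity population (SAP 5.3.2) requires that infants "have not received prophylactic treatment with palivizumab between birth and Day 180 after delivery". It does not mention RSV infection. Nor do the major-deviation list (SAP 5.3.3.1), the serology sample conventions (SAP 16.6) or Protocol 10.5. The correlate analysis (SAP 11.1.5) is the exception: it relates disease status to the immune level "before the onset of the first episode of a RSV infection".

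**The concern.** Enrolment is timed so that infants probably live through at least three months of RSV transmission (SAP 2), and infant sampling runs over the same months to D+180 (Protocol 7.2). The anti-F ELISA described in Protocol 7.2.1 detects human anti-F IgG and has no step that separates maternal from infant antibody. An infant that has been infected and has responded can therefore contribute a late value that has risen, while the model reads every value as residual maternal antibody.

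Two results follow. The fitted decline is too shallow, so the half-life comes out long. And infected placebo infants tend to lie in the upper tail that defines the SRR cut-off, so vaccine-group infants must exceed a threshold set partly by natural infection. The SAP already takes account of non-maternal antibody for palivizumab recipients and for the correlate analysis, but not here. SAP 16.4 says that the interpretation of the duration of protection will draw on immunogenicity results, so the late figures will be read.

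**Working it through.** **No stated figure is disputed.** The SAP gives no half-life or SRR value. The only figure to reproduce is the power that rests on the attack rate used below (SAP 13): 4% placebo, efficacy 65%, 2,786 and 1,432 infants, one-sided 0.0124, null efficacy 30%.
- Vaccine-arm rate: 0.04 × 0.35 = 0.014.
- SE of log RR = √[0.986/(2,786 × 0.014) + 0.96/(1,432 × 0.04)] = 0.205.
- Power = Φ(ln(0.70/0.35)/0.205 − 2.244) = 87.2%, against 87% stated.

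**Half-life.**

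From the documents: sampling at cord plus D14/D90, D35/D120 or D60/D180 (Protocol 7.2), pooled least squares, half-life = log10(2)/slope.

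Assumed: true half-life 40 days; a share p of infants infected evenly over Days 0-180; antibody raised f-fold from 14 days after infection; infection independent of antibody level; equal cohorts.

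The share boosted at age a is p(a − 14)/180, or zero before Day 14. Per unit p:

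| Cord | D14 | D35 | D60 | D90 | D120 | D180 |
|---|---|---|---|---|---|---|
| 0 | 0 | 0.117 | 0.256 | 0.422 | 0.589 | 0.922 |

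Regressed on age over the nine cohort-by-visit points, this has slope 166.25/32,254.2 = 0.005154. Hence

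estimated half-life = log10(2) / [log10(2)/40 − p × log10(f) × 0.005154].

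For example, with p = 0.028 and f = 4: 0.30103/(0.0075257 − 0.0000869) = 40.5 days.

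| Infected by Day 180 | 4-fold | 10-fold |
|---|---|---|
| 2.8% | 40.5 (+1.2%) | 40.8 (+2.0%) |
| 10% | 41.7 (+4.3%) | 42.9 (+7.4%) |

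The 2.8% doubles the plan's implied 1.4% vaccine-arm rate by Day 90. That rate counts only medically-significant LRTI, so all RSV infection can only be more frequent. How much more is not stated.

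The LLOQ rule pushes the same way: values that have decayed below LLOQ leave the regression, while boosted values stay. This is not included in the table.

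**Infant SRR.**

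Assumed: log10 SD 0.35; a true 3-fold vaccine excess at the visit; infected infants shifted by log10(f).

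- No infection: cut-off = 1.645 × 0.35 = 0.576 log10 above the placebo mean. SRR = 1 − Φ((0.576 − 0.477)/0.35) = 39%.
- With infection, the cut-off t solves (1 − p_P) × Φ(t/0.35) + p_P × Φ((t − log10 f)/0.35) = 0.95, where p_P is the placebo share infected. SRR is the vaccine-arm mixture above t.

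| Infected placebo / vaccine | 2-fold | 4-fold | 10-fold |
|---|---|---|---|
| 4% / 1.4% | 37% | 33% | 25% |
| 10% / 6% | 35% | 26% | 11% |

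At 4% / 1.4% the cut-off t is 0.598, 0.643 and 0.723 for the three boosts. Distortion thus begins below 5% infected and depends strongly on the boost. Cord values cannot be affected and D+14 hardly at all; the problem lies mainly from D+60 onward.

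**The case against.** The strongest reply is about weight. Protocol 10.5 calls the decay modelling exploratory and the immunogenicity analyses descriptive. SAP 16.4 applies no multiplicity control to them. The one immune analysis tied to disease already uses pre-onset levels. All of this is correct and limits the consequence, but it does not justify a stated rule that works against the SAP's own estimation target.

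The second reply is about size. The documents give no total infant infection rate, boost or half-life, and at the planned vaccine-arm rate the half-life bias is about 1-2%. That also stands: the direction is secure, the amount is not.

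The third is that censoring at infection is not a clean correction. If low-antibody infants are infected first, as the inverse relation sought in SAP 11.1.5 supposes, those left are selected. Simulations with that dependence gave 40.5-42.0 days after censoring, at 8-30% infected, for a true 40. For geometric means the trade-off is sharper: censoring conditions on an outcome that differs by arm, and raised the D+180 mean by 4-19% at 10-30% infected. All-observed levels by visit are a legitimate description, so they should remain the main table there.

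A reader might also infer that the half-lives of the two arms are not comparable. SAP 11.1.4 specifies no half-life contrast between arms, so this does not follow as a fault of the plan. Nor does it follow that once 5% of placebo infants are infected their response alone sets the cut-off: with a 2-fold boost the SRR at 10% / 6% is still 35%, against 39%.

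**Conclusion.** The omission is real: explicit for the half-life regression, and by absence of any rule for the infant SRR. The half-life is biased long and late vaccine-group seroresponse is understated.

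The illustrative size is +1-2% on the half-life at 2.8% infected and +4-7% at 10%, for a 4- to 10-fold boost. SRR falls from 39% to 33-25% at the plan's own 4% / 1.4% rates, or to about 37% with a 2-fold boost. The 40-day half-life, the boost, the infection timing, the 3-fold excess and the SD of 0.35 are all assumptions. The SRR is the more fragile of the two.

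It would be too strong to say that late infant results are dominated by natural infection; the documents do not give the infection rate or boost needed to show it. These are descriptive secondary analyses, and the primary efficacy conclusion does not depend on them.

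**What to change.** In SAP 11.1.4 and in the infant SRR of 11.1.1-11.1.3, including the placebo percentile, exclude infant samples drawn on or after the onset of the first RT-PCR-confirmed RSV episode, whether confirmed by study PCR or by a hospital record. Report the all-samples version as a sensitivity analysis.

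For infant geometric means and GMR AD/Cord, do the reverse: keep all samples as the main table and add the infection-censored version as a sensitivity analysis. Do not add a rule that drops values for rising within an infant, since that selects on the outcome.

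The cost is a few sentences and one derived flag. SAP 10.1 defines the RSV episode, 16.6 gives the onset-date rules, and 4.2.3.1 provides for capture of local RT-PCR results. The downside is small: some late samples are lost, infections never swabbed remain in the data, and some bias persists if low-antibody infants are infected first. The SAP should state these limits beside the result.

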7.2 Assessments of Immunogenicity

Anti-F IgG antibody levels in EU, PCA concentrations, and neutralizing antibody titers to RSV/A and RSV/B will be determined at protocol-specified time points for all subjects. Completion of microneutralization testing may be staged, due to its cumbersome nature, and results may be reported in addenda to the primary clinical study report. Serological immunogenicity parameters will include GMEU, geometric mean concentration (GMC), or GMT (as appropriate); GMFR, SCR, and SRR by treatment group for most analyses. Comparisons across groups will be performed as described in the statistical analysis plan and briefly in Section [10.5](#). Blood samples from maternal subjects will be drawn for RSV serology testing at screening (Day -28 to 0) and on Day 14 prior to delivery, at delivery, and on Days 35 and 180 post-delivery. Blood samples from infant subjects will be drawn for RSV serology testing at post-delivery study Days 14 and 90 for Cohort 1 infants, on Days 35 and 120 for Cohort 2 infants, and on Days 60 and 180 for Cohort 3 infants. Infant subjects may also have blood drawn within 72 hours of birth if cord blood is not collected at delivery.

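### The infant half-life regression pools repeated samples from the same infants with no provision for within-infant correlation, so its 95% CI is not assured to have nominal coverage and the slope is estimated inefficiently.

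*SAP*

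**What the plan says.** SAP 11.1.4 regresses log10 antibody level on the infant's actual age at sampling, in the PP-IMM-I population. Quantifiable values from every time-point and all three phlebotomy cohorts go into one fit; the sentence that lists them ends "Cohort 3) will be pooled to assess the persistence of anti-F IgG antibody, PCA, and/or MN levels over time". Values below the LLOQ are dropped. The inclusion rule begins "All measurements from subjects with at least two" and refers to values at or above the LLOQ. On the model it says "A conventional first order antibody decay model will be used for analysis", and it leaves room for a more complex decay curve. The half-life comes from the single slope, "with the corresponding 2-sided 95% confidence interval".

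Each infant can give up to three values. SAP 5.3.2 requires a cord sample (or a birth sample within 72 hours) for PP-IMM-I. Protocol 7.2 adds two later samples, "at post-delivery study Days 14 and 90 for Cohort 1 infants, on Days 35 and 120 for Cohort 2 infants", and Days 60 and 180 for Cohort 3.

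SAP 11.1.4 names no infant effect, correlation structure, clustering or robust variance. By contrast, SAP 10.3 to 10.5 name a robust variance keyed to the subject identifier for the efficacy models. Paired change is reported separately in SAP 11.1.1 as "within-subject ratios after delivery (AD) on D+14, D+35, D+60, D+90, D+120, and D+180 over cord blood value at delivery", but it does not feed the half-life.

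**The concern.** An infant who starts high tends to stay high, so that infant's two or three values are correlated. An ordinary pooled regression puts the between-infant spread into the residual and computes the slope's standard error as if each value were a separate infant. That standard error is correct only by coincidence.

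Estimating antibody decay in infants is a listed secondary objective (Protocol 2.2, SAP 4.1.2), and this half-life with its interval is the estimate that answers it. An interval labelled 95% should have that coverage. The sampling schedule also allows a sharper estimate than the pooled fit gives.

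**Working it through.** The documents state no half-life, slope, SE or within-infant correlation, so there is no planned figure to reproduce. The check computes the variance of the pooled slope on the planned schedule.

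**Inputs from the documents.** Sampling days are 0, 14, 90 (Cohort 1), 0, 35, 120 (Cohort 2) and 0, 60, 180 (Cohort 3), with cord taken as day 0.

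**Assumptions.** 2,700 infants, 900 per cohort, all three values quantifiable (the planned vaccine-arm per-protocol efficacy population in SAP 13 is 2,786). Half-life 40 d, so the slope is log10(2)/40 = 0.00753 log10 per day in size. Between-infant SD σb is 0.2-0.4 and residual SD σe is 0.10-0.15 log10.

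**Age spread.**
- Mean age is 499/9 = 55.44 d.
- The sum of squares for one infant per cohort is 32,254, of which 29,107 (90%) lies within infants.
- Sxx = 900 × 32,254 = 29.03 million.

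**Worked case: σb 0.3, σe 0.1, common decay rate.**
- Naive SE = √[(0.09 + 0.01)/29.03 million] = 5.87 × 10⁻⁵.
- True SE of the same slope = √[σe²·Sxx + σb²·ΣT²]/Sxx, where T is an infant's summed age deviation: −62.3, −11.3 and 73.7 in the three cohorts. ΣT² = 900 × 9,441 = 8.50 million. This gives √(290,288 + 764,694)/29.03 million = 3.54 × 10⁻⁵.
- Naive/true = 5.87/3.54 = 1.66.
- Random-intercept SE = 1.95 × 10⁻⁵, essentially 0.1/√(900 × 29,107).
- Half-width for the half-life = 1.96 × SE × 40/0.00753, which gives 0.61 d (naive), 0.37 d (correct interval for the pooled slope) and 0.20 d (random intercept).

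**Across the assumed SDs.** Each cell is the naive/true SE ratio. The CV is that of the decay rate between infants, uncorrelated with starting level. The last column is the random-intercept CI width relative to the naive one at CV 0.

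| σb / σe | CV 0 | CV 20% | CV 30% | Relative width |
|---|---|---|---|---|
| 0.2 / 0.10 | 1.52 | 1.03 | 0.87 | 47% |
| 0.2 / 0.15 | 1.35 | 1.02 | 0.88 | 63% |
| 0.3 / 0.10 | 1.66 | 1.23 | 1.03 | 33% |
| 0.3 / 0.15 | 1.52 | 1.20 | 1.03 | 47% |
| 0.4 / 0.10 | 1.73 | 1.38 | 1.18 | 26% |
| 0.4 / 0.15 | 1.62 | 1.34 | 1.16 | 37% |

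**Coverage check.** In a simulation of 300 infants (1,500 replicates, SD 0.3 at birth, cord plus two samples), the naive 95% CI covered 98.5%, 99.5% and 100% at intraclass correlations of 0.5, 0.7 and 0.9 with a common decay rate. At a decay-rate CV of 30% it covered 93.5% to 94.5%. At an intraclass correlation of 0.2 and CV 30%, the computed SE ratio is 0.86.

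**If the cord value is left out.** With only the two later samples and a common decay rate, the ratio is 1.05 to 1.33 at intraclass correlations of 0.2 to 0.9.

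**The case against.** The strongest reply is that this hardly matters. Protocol 10.5 calls immunogenicity analyses descriptive and the decay modelling exploratory. No threshold or decision uses the interval. In the worked case the half-width is 0.61 d on 40 d, about 1.5%, and the error is conservative. That stands, and it limits the point to a minor one.

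Four stronger readings are tempting, and the documents do not support them.

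- **The interval is too wide.** This follows only if infants differ mainly in starting level and share a decay rate. With decay-rate variation the ratio passes through 1 and below it, and no variance figures are given to settle the direction.
- **The paired information is wasted.** About 90% of the age sum of squares lies within infants, so pooled least squares does use the within-infant decline, though with poor weights. The ratios to cord also report it directly, and SAP 11.1.2 and 11.1.3 carry them to PCA and MN.
- **The two arms are pooled.** SAP 11.1.4 names no treatment term, but it describes decay of antibody resulting from vaccination, and SAP 11.1 summarises outcomes by treatment group. Pooling of arms is conjecture.
- **The SAP declares the values independent.** It does not say so. That is the natural reading of a pooled conventional regression with no correlation specified.

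**Conclusion.** The point holds as a defect in a stated method. Followed as written, SAP 11.1.4 yields a half-life interval whose coverage is not assured and a slope less precise than the samples allow.

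Its size depends on assumptions. With a common decay rate and the SDs above, the naive SE is 1.35-1.73 times the true SE, and a random-intercept CI is 26-63% as wide. With a decay-rate CV of 20-30%, the SE ratio is 0.87-1.38. The ratios do not depend on the number of infants, but the widths do. For a subset of 300, all widths are √(2,700/300) = 3 times larger, so 0.61 d becomes 1.83 d. That could matter for MN, which may be run on a subset, but applying these SDs to MN is a further assumption. The effect is confined to the decay objective; the efficacy conclusion is untouched.

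**What to change.** In SAP 11.1.4, specify a linear mixed model of log10 antibody on actual age, with a random intercept per infant and a random slope if estimable, fitted by treatment group. Report half-life = −log10(2)/slope with the model-based 95% CI; the formula as printed gives a negative value when antibody declines. State whether the cord or birth value enters the fit.

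The minimum alternative is to keep the pooled slope and use infant-clustered robust standard errors. That addresses coverage but not efficiency: in the worked case the half-width would be about 0.37 d rather than 0.20 d.

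The cost is a few lines of SAP text and a standard SAS procedure on the same data, with no new samples or visits.
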